Intervention (adherence/compliance)	
 
1. Number of participants accessing all online lessons
 
2. Use of health coaches (PACT arm)
 
3. Pain and risk assessment instruments within the PACT program (PACT arm)
 
4. Time spent in online program per week (PACT arm)
 
	
 
1. 80% of enrolled participants access all lessons as measured by Web site hits
 
2. 90% of participants in PACT have at least 3 phone meetings with the health coach (PACT arm)
 
3. Completion of all pain and risk assessment instruments within the PACT program (PACT arm)
 
4. Time spent in each module of online program per week (PACT arm)
 

- c. Completion of questionnaires at 8-week and 16-week follow-ups, and program evaluation. Completion of questionnaires will be measured by the percent of participants who complete the 8-week and 16-week follow-up questionnaires and, the program evaluation. We expect that at least 80% of participants will complete all questionnaires.

Objective	Constructs	Target outcomes
Evaluation (adherence/compliance)	
 
1. Number of participants completing 8-week and 16-week follow-up questionnaires
 
2. Number of participants completing the program evaluation survey questions (PACT arm)
 
	
 
1. 80% complete both 8- and 16-week follow-up questionnaires
 
2. 80% of participants in PACT group complete the program evaluation form
 

Evaluation (instrument performance)	
 
1. Responsiveness to constructs in subscales of the survey.
 
2. Inter-correlations between scales
 
3. Participant burden is measured by time to complete.
 
	
 
1. Outcome variables show changes in the expected direction
 
2. Outcome variables are associated with mediator/moderator factors in the expected direction
 
3. 90% of participants complete all surveys in estimated time
 

- d. Participant perceptions of the online website functionality and acceptability will be measured by participant reports of problems and ease of use reported at the program

evaluation. These reports will come from the number of phone calls/questions received about web-site issues, and from the qualitative interview.

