Objective	Constructs	Target outcomes for both arms
Web-Site functionality	
 
1. Heuristic evaluation of functionality of the Web-based platform
 
2. Mode of administration acceptance
 
	
 
1. Less than 10% of participants note problems with website via comments section in each module or during program evaluation
 
2. 90% of participants rate web-site accessibility for learning the concepts as very good to excellent
 

Intervention (acceptability)	
 
1. Identification of self-reported barriers for improvement
 
2. Pace in which participants complete the program
 
	
 
1. 80% of participants identify at least one self-report barrier for improvement
 
2. 60% of participants follow the timeline on the Web site to complete in 8 weeks
 

Participant perceptions of program	
 
1. Qualitative interviews of participants
 
	
 
1. At least ten randomly selected participants will agree to be interviewed to provide their perceptions about the content of the program and at least 90% report that it is acceptable.
 

- e. Participant perception of health coaches in the PACT program will be evaluated by qualitative interviews of both health coaches and participants

Objective	Constructs	Target outcomes for both arms
Participant perceptions of health coach	
 
1. Qualitative interviews of participants about health coaches
 
	
 
1. At least ten randomly selected participants will agree to be interviewed to provide their perceptions about the content of the program. Of at least 10 participants interviewed, 90% will report that they found the health coaches to be helpful.
 

---

Health coach perception of program	1. Qualitative interviews of participants	1. Health coaches will provide their perceptions on the program and areas for development
------------------------------------	---	---

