## 7 STUDY PROCEDURES/EVALUATIONS

### 7.1 Study Procedures/Evaluations

#### 7.1.1 Outcome Measure Questionnaires

The questionnaires that will be utilized are briefly described below. Copies of the questionnaires are reproduced in the appendix. All of the questionnaires are self-administered except for the qualitative interview which is conducted via phone by the study coordinator. For outcome measure questionnaires, responses will be recorded electronically through the study website.

Telephone Screen. This is a method used to screen for TMD pain. This questionnaire will be completed baseline and repeated at the final study visits.

Pain severity and Pain Interference. The Graded Chronic Pain Scale (GCPS) assesses 2 dimensions of pain: pain intensity and pain-related disability with mean intensity ratings for reported current, worst, and average pain.

Jaw Functioning. Jaw Functional Limitation Scale (JFLS-8) identifies daily activities interfered with by jaw pain. This 20-item instrument measures limitations across 3 domains: mastication (6 items), vertical jaw mobility (4 items), and verbal and emotional expression (8 items). Two items are not scored as part of these 3 subscales. A degree of limitation is rated on a 0-10 scale from 0 ("no limitation") to 10 ("severe limitation").

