## **7.1.2 Program Evaluation and Qualitative Interview**

### **7.1.2.1 Program Evaluation**

As part of the 8-week follow up survey, the program evaluation involves 7 close-ended questions to assess participant experience with the overall program and an additional 11 close ended questions for participants involved in the PACT program to assess satisfaction and perceptions of the program.

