### **7.1.2.3 Website issues**

Phone calls and questions received about web-site issues will be documented throughout the study to assess functionality of the website.

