## 8 ASSESSMENT OF SAFETY

We will implement a meaningful safety system for the study by considering the risks of the study intervention, study procedures as well as the characteristics of the study population (individuals with TMD pain). There are no risks to other individuals in the study such as health coaches.

Specifications of Safety Parameters that will be recorded by the Study Coordinator for each participant in their research record include;

- The study coordinator will be in frequent contact with the health coaches to identify any potential participant concerns with study staff.
- The participants also have the phone number for the study coordinator to call if a concern related to the study program arises.

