to address any issues. Application can be monitored via alerting and monitoring tools that send notification to the system administrator whenever the application becomes inaccessible. Application uses open source version control system like SVN for source code version maintenance.

Application development uses the following tools/technologies/languages: Java, J2EE, JSP, Spring MVC Framework, Spring Security Framework, J2EE design patterns, jQuery, AJAX, Bootstrap framework, JavaScript, Oracle SQL/PLSQL, Log4j, jFree chart, JUnit, Apache Tomcat V7.0, Shell script, SVN, REDCap.

*Control Flow:* User log-in to the system using their unique user-id and password. For study participants after login, system presents a brief intro of study along with consent form. User gives his/her consent which is stored in the system data base; system then navigates to initial baseline survey form. Upon successful completion of the survey the survey results are stored in the database and based on pre-identified criteria system randomly assigns user to Usual-self-care arm or PACT arm; system takes user to their respective arm's program page. In the program page user has the opportunity to learn through the study modules. Based on user arm type, study modules present self-management lessons in the form of videos or slides. Once user completes the modules, then system prompts user to complete periodic (2month, 4month) surveys. The survey responses are stored in database and analyzed later to understand how the program has helped participants in improving TMD pain. Users of the application can use the contact information provided in the consent form to contact study coordinator in case of any navigation issues or application accessibility issues. Users can get new password/reset one using "forgot password" links.

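### The website-problem target leaves out the logged telephone calls and questions that the protocol names as a source for website functionality, so it leans towards being met

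*Protocol*

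**What the plan says.** The table in protocol section 3.2.1(d) gives the first website-functionality target, under a column heading that applies it to both arms: "Less than 10% of participants note problems with website via comments section in each module or during program evaluation".

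The paragraph introducing that table says that website functionality will be measured by participants' reports of problems and of ease of use at the program evaluation. It then says: "These reports will come from the number of phone calls/questions received about web-site issues, and from the qualitative interview".

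Section 7.1.2.3 adds: "Phone calls and questions received about web-site issues will be documented throughout the study to assess functionality of the website".

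Appendix B (description of the website, control flow) says that users can use the contact details in the consent form to "contact study coordinator in case of any navigation issues or application accessibility issues". Section 8 says: "The participants also have the phone number for the study coordinator to call if a concern related to the study program arises".

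On the program evaluation, section 7.1.2.1 says: "As part of the 8-week follow up survey, the program evaluation involves 7 close-ended questions", with 11 further closed questions for PACT. For the outcome questionnaires, section 7.1.1 says that "responses will be recorded electronically through the study website".

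The SAP does not define a numerator, a denominator, or a way of combining sources for this target.

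**The concern.** The protocol names one set of sources for website problems and scores its target on another. The log of calls and questions is kept expressly to judge functionality, but no target uses it.

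The omission works in one direction. Both counted routes need a site that works for the participant: the comments boxes sit inside the modules, and the evaluation is part of the online week-8 survey. In the PACT arm an unfinished lesson also blocks all later material (section 6.3 B). Someone stopped part-way may leave no comment and no evaluation, and a logged call does not bring that person into the count.

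The counted routes may also pick up problems unequally by arm. In Appendix G the evaluation items given to everyone are closed, and the only one on access is item 22g. The open questions, 26 and 27, are on the PACT form only. They ask about likes and suggestions, so their effect on this target is probably small.

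Feasibility and acceptability are the primary outcomes of this pilot (section 11.4 and the SAP), and website functionality is one of the methods being tested for the multisite trial. A target that misses some of the recorded problems gives that trial too favourable a starting figure.

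**Working it through.** **Inputs from the documents**
- Limit: below 10% of participants; counted routes are module comments and program evaluation (3.2.1(d)).
- Planned sample: 80, with 40 per arm (section 11.2).
- Related targets: 95% start the program, 80% access all lessons, 80% fill in both follow-up surveys (3.2.1(a) to (c)).

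**Inputs assumed**
- Denominator of 80, all randomised. The target names none.
- p, the true share of participants with a website problem after randomisation.
- v, the share of those participants who appear in a counted route.

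The documents give neither p nor v, so a range is shown. The 10% limit is a chosen target, so the plan has no derivation to reproduce.

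**Step 1: what the limit allows.** The largest k with k/n < 0.10:
- n = 80: 7/80 = 8.75% meets the target; 8/80 = 10% does not. At most 7.
- n = 64 (80% of 80 respond): 6/64 = 9.4%; 7/64 = 10.9%. At most 6.
- n = 40 (one arm): 3/40 = 7.5%; 4/40 = 10%. At most 3.

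**Step 2: chance that the target is met.** The number counted is taken as X ~ Binomial(80, p × v), and the target is met when X ≤ 7.

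| p | v = 1 | v = 0.75 | v = 0.5 | v = 0.25 |
|---|---|---|---|---|
| 10% | 0.446 | 0.750 | 0.953 | 0.999 |
| 15% | 0.073 | 0.310 | 0.750 | 0.990 |
| 20% | 0.005 | 0.073 | 0.446 | 0.953 |
| 25% | <0.001 | 0.011 | 0.202 | 0.873 |

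The column v = 1 is the result when every affected participant is counted, whichever route the report took.

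**Step 3: the same point as a count.** Seven participants in the counted routes give 7/80 = 8.75%, which meets the target. With 8 more who only telephoned, the figure is (7 + 8)/80 = 15/80 = 18.75%, which does not. The 8 are an illustration, not a forecast.

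**Step 4: how far the other targets cover the gap.**
- Start: 5% of 80 = 4 participants may fail to start.
- All lessons accessed: 20% of 80 = 16 may fall short.
- Both follow-up surveys: 16 may miss at least one.

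These limits would show widespread access failure, but none of them says whether the website was the reason.

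**The case against.** The strongest reply is that the text can be read as already including the calls. The introductory sentence speaks of problems reported at the program evaluation and then says that those reports come from calls, questions and the interview. Section 7.1.2 puts the call log under a heading that covers program evaluation. On that reading, the target's mention of program evaluation takes in the log. This is arguable. Against it, section 7.1.2.1 describes the program evaluation as closed questions within the 8-week survey, and section 6.4 describes it in the same way. A programmer following the target line would count survey answers and comments. The ambiguity is itself a reason to amend the line.

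A reader might also infer that the target could be met while many participants cannot use the site at all. The documents do not support that. Randomisation follows login, electronic consent and the baseline survey on the same website (sections 5.4.1 and 6.2), so the gap concerns later access, navigation and module problems. Widespread failure would show in the start, lesson-access and survey targets. Staff also call people who fall behind (sections 6, 6.3 B and 6.4), and there is a password reset link. The companion target, that 90% rate accessibility very good to excellent, adds less, because no evaluation item printed in Appendix G uses that scale.

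Nor do the documents make this target a go/no-go gate. The analysis is descriptive, and nothing stops the log from being reported separately.

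Three further points stand. Appendix B says that users can contact the coordinator, not that they must. A caller may also leave a comment or disagree with item 22g, so only people who report by telephone alone are lost. And a raw log mixes faults with routine questions, so a problem must be defined before calls are counted.

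**Conclusion.** The mismatch is real and should be corrected. On its most natural reading, the target leaves out a source that the protocol names for website functionality, and the omission can only lower the count. The target therefore leans towards being met, by an amount that the documents do not allow one to estimate. Under the assumptions above (80 in the denominator, independent participants, half of those affected visible), the chance of meeting it rises from about 0.07 to 0.75 at a true rate of 15%, and from about 0.005 to 0.45 at 20%. If nearly all callers also comment or disagree with item 22g, the effect is small.

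The point goes no further than this: some recorded problems fall outside the criterion meant to summarise them, and the other targets are only a partial backstop because they cannot attribute a failure to the website.

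**What to change.** Amend the first website-functionality target in section 3.2.1(d), and add the matching tabulation to the SAP, as follows.

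- **Numerator:** randomised participants, each counted once, with at least one website malfunction, access problem or navigation problem. Routine how-to questions are excluded.
- **Sources:** any of the call and question log, module comments, the program evaluation (including disagreement or strong disagreement with item 22g), the qualitative interview, and the coach logs. Coach logs are included because coaches help PACT participants with the technology (section 5.8), so some problems may reach them rather than the coordinator.
- **Denominator:** all randomised participants. State how many did not complete the evaluation.
- **Presentation:** overall, by arm and by source, since coach logs and the interview guide in Appendix H relate to PACT only. Show the count from comments and evaluation alone beside it.
- **Limit:** keep 10%.

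The cost is one amended line, one table and a small coding task to separate problems from routine questions. No new data collection is needed: contacts with the coordinator are already to be documented (section 6.6) and calls tracked (section 15.1). The figure will probably be less favourable, and the unchanged 10% limit becomes harder to meet. That is acceptable, because the wider count follows the sources that the introductory text already names.

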#### 3.2.3.2 Hypothesized moderators

Of the 80 patients participating in the study, we believe that 90% will complete the moderator measures at baseline and all follow-up periods and report the burden of completing these is acceptable. Specific measures of disability status, catastrophizing, depression, oral habits, perceived stress, and social support will be made by questionnaires, as described in section 8.1.1.

Outcome Measures including Data Constructs, Scales, Sources and intervals.								
	Construct	Scale/ Variable	Data Source	Target	Baseline	Intervention	Weeks from baseline	Weeks from baseline
Timing (weeks)					At Enrollment	0-8 wks.	8 wks.	16 wks.
Screening	Eligibility	DC-TMD Pain Screener and self-report criteria	Phone Screen	Potential participants screened	X			
	Demo-graphics	Age, marital status, education, employment,	Phone screen	Potential participants screened	X			

Outcome Measures including Data Constructs, Scales, Sources and intervals.								
	Construct	Scale/ Variable	Data Source	Target	Baseline	Intervention	Weeks from baseline	Weeks from baseline
Timing (weeks)					At Enrollment	0-8 wks.	8 wks.	16 wks.
Other Descriptive Information	Prior Medical Conditions	Prior Medical Conditions	On-line survey	Participants	X			
Objective 1 Process Evaluation	Recruitment	Contact/consent	Survey Center logs	Participants	X			
	Compliance/adherence	Self-report of intervention practice	On-line Survey	Participants		X		
	Compliance/adherence	Program evaluation form	On-line survey	Participants			X	
	Acceptability	Heuristic evaluation of ease of use and functionality	Web hits Survey	Participants			X	
	Participant experience	Barriers and facilitators to adherence	Qualitative interview	Participants		X	X	X
Objective 2 Primary Outcomes	Pain Severity	Graded Chronic Pain Scale-severity (7 items; of 10)	On-line survey	Participants	X	X	X	X
	Jaw Function	Jaw Functional Limitation Scale (JFLS-8; items; short version)	On-line survey	Participants	X	X	X	X
Objective 2 Secondary Pain Outcomes	Pain interference	Graded Chronic Pain Scale-intensity (3 items of 10)	On-line survey	Participants	X	X	X	X
Objective 3 Mediators	Self-efficacy	Chronic Pain Self-efficacy Questionnaire (5 item Self-efficacy for Pain management (PSE) scale)	On-line survey	Participants	X	X	X	X

Outcome Measures including Data Constructs, Scales, Sources and intervals.								

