### **7.1.2.2 Qualitative Interview of Participants**

At least 10 randomly selected participants will be asked to complete the qualitative interview. The qualitative interview involves 9 open-ended questions to assess participants' satisfaction and perceptions of the program.

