24. To what degree did was each of the following features/components of the PACT Self-Care program helpful in contributing to your learning?

	Not at all Helpful	Somewhat Helpful	Helpful	Very Helpful	Extremely Helpful	NA
a. Video lessons						
b. Narrated PowerPoint presentations						
c. Graphic Illustrations						
d. Presentations by [name]						
e. Self-assessments at the end of each module						
f. Online animated characters used to support learning						
g. Recommended exercises and activities in each module.						

25. To what degree did the follow three aspects of the PACT Self-Care program help you in your learning?

	Not at all Helpful	Somewhat Helpful	Helpful	Very Helpful	Extremely Helpful	NA
a. Daily pauses						
b. Calming activities						
c. Helpful habits						

26. What did you like most about the program?

27. What suggestions do you have for improving the online PACT Self-Care program?

28. In addition to the 8 week survey, some participants will be selected for a more in-depth interview about their experience in the TMD Self-Care Study. The phone interview would take 20-30 minutes and would be scheduled at a time that was convenient for you. All feedback would be confidential and you would receive a \$25 Target gift card as a thank you for your time. If you are selected, would you be interested in participating in this conversation?

Yes I would be interested.

Preferred contact phone number \_\_\_\_\_

**Thank you for participating in this study and completing this survey.  
We will be mailing you a \$35 dollar Target gift card as a thank you for  
completing this survey.**

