**We will be mailing you a \$45 dollar Target gift card as a thank you for completing this survey.**

**APPENDIX H. QUALITATIVE INTERVIEW  
(FOR PACT STUDY INTERVENTION PARTICIPANTS)**

Thank you for agreeing to take the time to talk with me about your participation in the TMD Self-Care Study. We are particularly interested in your perceptions about the PACT Program as we continue to work on developing and improving the program. This interview will take approximately 20-30 minutes. All feedback you provide will be confidential and you will receive a \$25 Target gift card as a thank you for your time.

1. I would like to start by asking you to tell me about your overall thoughts about the PACT Program? What did you think about it?
2. How has the PACT program affected the way you think about your TMD pain
3. How has the PACT program affected how you manage your TMD pain?
4. What did you learn from the PACT program that was new to you?
5. Have you made any changes in your life as a result of your participation in the PACT program? If yes, please tell me about them.
6. What did you learn in the PACT program that continues to be helpful to you in managing your TMD pain?

PROBE: Are there specific ways you take care of yourself now based on what you learned from the PACT program?

7. Considering your life in general, what do you think has changed for you as a result of your participation in the PACT program?
8. Has your reaction to stressful situations changed as a result of participating in the PACT program?
9. Please tell me about your experience with your health coach.

PROBES:

- a. What was the most helpful part of having a phone coach?
- b. How frequently did you meet with the coach?

- c. What did you find difficult about working with the health coach?
  - d. Do you think your opinion of the PACT program would change if the health coach was not a part of the program?
10. Considering your participation in the PACT program what were the least helpful parts of the program?
11. What parts of the program were the most helpful for you?
12. If you could make a change to the PACT program what would it be?
13. Of the seven main modules, which were the most effective for you?  
PROBES: to remind you the 7 modules are Body, Lifestyle, Mind, Emotions, Spirit, Social Life and Environment
14. What parts of your **Action Plan** were most helpful? (Health habits, daily pauses, and calming practice were the 3 main components of the action plan).

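### The 90% coach-helpfulness target is judged on as few as ten PACT interviewees from an unstated sampling frame, while the week-8 survey sent to the whole PACT arm has no closed item on the coach

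*Protocol*

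**What the plan says.** Section 3.2.1(e) of the protocol states that perception of the coaches "will be evaluated by qualitative interviews of both health coaches and participants", and sets the target: "Of at least 10 participants interviewed, 90% will report that they found the health coaches to be helpful". Section 3.2.1(d) puts a matching mark on program content among at least ten randomly selected interviewees: "and at least 90% report that it is acceptable".

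On selection, section 7.1.2.2 says only that "At least 10 randomly selected participants will be asked to complete the qualitative interview". Sections 4 and 6.4 also call the choice random. None of them says from which list the names are drawn. The guide in Appendix H is headed "FOR PACT STUDY INTERVENTION PARTICIPANTS", so interviewees come from the PACT arm.

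The one invitation in the documents is item 28, the last item of the PACT-only week-8 survey in Appendix G: "If you are selected, would you be interested in participating in this conversation". A yes is followed by a phone number. The other week-8 form has no such item.

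In the same PACT survey, item 24 asks about "each of the following features/components of the PACT Self-Care program helpful in contributing to your learning". Its rows cover videos, slides, graphics, the presenter, self-assessments, animated characters and exercises. Item 25 covers pauses, calming and habits. No closed row in items 22 to 25 mentions the coach.

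The SAP names acceptability and feasibility as primary outcomes. It gives no denominator, interval or coding rule for these targets.

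**The concern.** Coaching is one of the components that most separates the arms, and Objective 1(e) is devoted to it. The verdict on whether participants found it helpful nevertheless hangs on a handful of interviews. A form that could ask the question already goes to the whole PACT arm.

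Two separate weaknesses follow. The first is precision: ten answers cannot tell a 90% coach from an 80% coach. The second is possible selection: if item 28 is the route to interview, people who do not return the week-8 survey cannot be chosen, and those who do return it must volunteer. They may be the more satisfied ones. A favourable result could then carry a coaching model into a multi-site trial on weak evidence.

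In addition, the coach question in Appendix H (item 9) is open-ended with probes. Turning the answers into a percentage who found the coach helpful needs a coding rule that neither document gives.

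**Working it through.** **Inputs.** Pass mark 90% and minimum ten interviewees (section 3.2.1(d) and (e)); 40 participants per arm (section 11.2); 80% of PACT participants completing the program evaluation (section 3.2.1(c)), i.e. 0.80 × 40 = 32. The plan gives no calculation behind the number ten, so there is none to reproduce.

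**1. Pass mark.** 0.90 × 10 = 9, so the rule at the minimum is at least 9 of 10. On 32 survey answers, 0.90 × 32 = 28.8, so at least 29.

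**2. Precision.** Exact (Clopper-Pearson) 95% intervals:
- 9/10: 55.5% to 99.7%
- 29/32: 75.0% to 98.0%

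**3. Chance of meeting the target.** For ten interviews, P(X ≥ 9) = 10p⁹(1 − p) + p¹⁰. At p = 0.80 this is 0.268 + 0.107 = 0.376. The survey column is the binomial tail P(X ≥ 29) with n = 32.

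| True rate | 9 of 10 | 29 of 32 |
|---|---|---|
| 70% | 0.149 | 0.0055 |
| 80% | 0.376 | 0.093 |
| 90% | 0.736 | 0.600 |

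Treating the ten as drawn without replacement from an arm of 40 changes little: if 32 of 40 find the coach helpful, the rule is met with probability 0.34.

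**4. Selection, if only survey returners can be drawn.** Assume 80% return the survey (the plan's own target). Let a be the rate among returners and q the rate among non-returners; the documents give neither. Whole-arm rate = 0.8a + 0.2q.

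| q | a = 95% | a = 90% |
|---|---|---|
| 50% | 86% | 82% |
| 70% | 90% | 86% |
| 80% | 92% | 88% |

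With a = 95%, the arm falls below 90% only if q is below (90 − 76)/0.2 = 70%. With a = 90%, any q below 90% does it.

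**5. Effect on the verdict at a = 95%, q = 50%.** Ten returners meet 9 of 10 with probability 0.91. Ten drawn at random from the whole arm (86%) meet it with probability 0.58.

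**6. What a survey row does and does not cure.** The same returners answer it. At a = 95% they reach 29 of 32 with probability 0.93, against 0.91 for ten interviews. The row narrows the interval but does not move its centre.

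**The case against.** The strongest reply is that several harsher readings go beyond the text, and it is right about each.

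- *Interviewees are reached only through item 28, so drop-outs are excluded.* This is an inference. No section confines the random draw to those who tick yes. The outcome table in section 3.2.3 also marks the interview during weeks 0 to 8, before item 28 exists, and Appendix A places it at week 16. Under section 6.5, a discontinued participant may, with permission, go through the final-visit procedures, which include the survey. What the documents do support is that the sampling frame is unstated and item 28 is the only route shown.
- *Participants who stall never get the survey.* Appendix B describes survey prompts after the modules are completed, but section 6.4 says all participants are asked and reminded.
- *Barriers are asked mainly of people who adhered.* The section 3.2.3 table does list the interview as the source for "Barriers and facilitators to adherence". However, barriers and problems are also sought in coordinator calls to those who fall behind (sections 6.3 and 6.4), at withdrawal (section 5.5.2) and in coach logs (section 5.8).
- *Content acceptability rests on ten people.* The formal 90% mark does. Content itself is rated by all PACT respondents in items 22 to 25.
- *Everything known about coaching rests on ten people.* Section 3.2.1(b) has an arm-wide target for three coach calls, coaches are interviewed, and free-text items 26 and 27 go to all PACT participants. None of these measures whether participants found the coach helpful in a form that feeds the 90% mark.

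Ten is also a floor, and more interviews would narrow the interval. What survives is the narrow point: the coach target has no arm-wide measure, and its interview sample has no stated frame.

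**Conclusion.** The concern holds in limited form. The precision problem is certain at the stated minimum: 9/10 is compatible with anything from 55% to 99.7%, and a coach whom 80% find helpful passes 38% of the time. One survey row at the plan's own 80% return would cut that to 9%.

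The selection problem is conditional. It arises only if the draw is confined to people who tick yes on item 28, which the documents suggest but do not state. Its size depends on the unmeasured views of non-returners. With 95% among returners, the whole-arm rate runs from 86% to 92% as non-returners go from 50% to 80%, so a shortfall below 90% is possible but not shown. Neither the 80% return nor the rates in each group are observed.

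**What to change.** 1. **Add one row to item 24** of the PACT week-8 survey, 'Telephone health coach calls', and state which response categories count as helpful. Judge the 90% coach target on all PACT respondents. Report the number of non-respondents and a sensitivity result that counts them as not helpful. With 29 of 32 favourable, that gives 29/40 = 72.5%. With 32 returns it cannot exceed 32/40 = 80%, so read it as a lower bound and not against the 90% mark. This step improves precision; it does not by itself remove non-response selection.

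2. **State the interview frame.** Draw the list by simple random sampling from all participants randomised to PACT, leaving out those who withdrew consent, since section 5.5.1 rules out further data collection from them. Invite those drawn whether or not they returned the week-8 survey. Report the numbers invited, agreed and interviewed.

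3. **If the list is stratified by lesson completion**, report the strata separately or weight them to arm proportions, and do not apply the raw 90% mark to the pooled interviews. Taking completers at 95% and non-completers at 50%, five of each gives an expected (95 + 50)/2 = 72.5%, and 9 of 10 is reached only about 15% of the time although the whole arm is at 86%.

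The cost is one survey row and a different sampling list, with the same minimum number of interviews. The downside is that non-completers are harder to reach and the figures may come out lower.
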